## **2.2. PRIMARY OUTCOME MEASURES**

The primary outcome of the study will be changes in the CAPS-5 total symptom scores between baseline and 8 weeks. The CAPS-5 is the gold standard in clinical PTSD assessment, and it is a 30-item structured interview that corresponds to the DSM-5 criteria for PTSD. For each item, standardized questions and probes are provided; total scores range from 0 to 80. CAPS-5 requires the identification of a single index trauma to serve as the basis of symptom inquiry.

## **2.3. SECONDARY OUTCOME MEASURES**

### **2.3.1. PCL-5.**

The PCL-5 is a 20-item self-report measure that assesses the 20 DSM-5 symptoms of PTSD. Its purposes include screening for PTSD and/or provisional diagnosis, and monitoring symptom change before, during, and after treatment. A total symptom severity score ranging from 0 to 80 is possible (Weathers et al., 2013). The PCL-5 will be administered at baseline to establish a baseline score in support of secondary objective 1.

### **2.3.2. PCL-C (PTSD symptoms)**

This standardized assessment comprised 17 items corresponding to the key symptoms of PTSD from the DSM-IV. The total symptom severity score ranges from 17 to 85. The PCL-C has been thoroughly validated and deemed reliable (Weathers, Litz, Herman, Huska, & Keane, 1994). The PCL-C will be administered at baseline in order to establish a baseline score in support of secondary objective 1.

### **2.3.3. MINI-INTERNATIONAL NEUROPSYCHIATRIC INTERVIEW (M.I.N.I.)-PLUS SUICIDALITY MODULE**

The M.I.N.I.-Plus is a structured interview for diagnosing DSM-IV and ICD-10 psychiatric disorders (Sheehan et al., 1998). This assessment will be administered at each follow-up (weeks 2, 4, 6, and 8). Response options are dichotomous (yes/no) and questions ask about desire, thoughts, planning, taking steps toward, and attempting suicide as well as deliberate injury without intent to kill oneself. The set of 7 items employs a complex automated scoring algorithm, with each item representing a different point value. For example, an affirmative response to the question about wanting to harm oneself carries a value of 2 points, while a positive response to the question about taking active steps toward preparing to injure or kill oneself carries a value of 9 points. Individuals scoring nine points or greater will be asked to complete an additional 4 questions regarding any *current* desire to harm themselves, thoughts

about suicide, plans for suicide, and active steps they may be taking. These four items will be used only for clinical purposes by a behavioral health clinician on call, as discussed below.

The suicidal ideation items from the M.I.N.I.-Plus serves to monitor participant safety during the course of their participation in the study, particularly since the 4-, 6-, and 8-week follow-up assessments will be administered online and completed by participants on their own (i.e., not in the study RC's office). If an individual should score 9 or greater on the M.I.N.I.-Plus items, they will be asked an additional 4 questions regarding *current* suicidal ideation or plans.

#### **2.3.4. AUDIT-C/AUDIT.**

The Alcohol Use Disorders Identification Test (AUDIT; Babor, Higgins-Biddle, Saunders, & Monteiro, 2001) will be used to assess potential alcohol abuse symptoms. The instrument was developed as a means of brief assessment and screening for excessive drinking. This 10-item scale is widely used and has been shown to be consistent with ICD-10 definitions for alcohol dependence and harmful alcohol use (Allen, Litten, Fertig, & Babor, 1997; Saunders, Aasland, Amundsen, & Grant, 1993). Scores range from 0 to 40, with scores between 8 and 15 (inclusive) suggest a medium level of alcohol problems, scores ranging from 16 to 19 represent a high risk of alcohol problems, and scores of 20 or greater warrant further diagnostic evaluation for alcohol dependence.

The AUDIT-C (AUDIT alcohol consumption questions) consists of the first 3 items of the full AUDIT and assess frequency of drinking, typical quantity, and frequency of heavy drinking. Based on a scale of 0 to 12, a score of 4 or greater is considered positive in males, while a score of 3 or more is positive among females.

#### **2.3.5. K6**

The K6 was developed for use in the U.S. National Health Interview Survey (NHIS) as a means of assessing nonspecific psychological distress. Scores range from 0 to 24 resulting from 6 items administered on a scale of 0 to 4, with a score of 13 or greater are indicative of serious psychological distress in the U.S. general population (Kessler et al., 2003).

#### **2.3.6. PHQ-9**

Depression symptoms will be assessed using the validated PHQ-9 (Kroenke, Spitzer, & Williams, 2001) in support of secondary objective 2. The PHQ-9 was developed as a short form of the full Patient Health Questionnaire (which was a self-administered version of the PRIME-MD instrument). Severity scores range from 0 to 27, with a score of 5 to 9 representing mild depression, a score of 10 to 14 representing moderate depression, and a score of 15 or greater representing a severe level of depression. Scores of 10 or greater are considered a "yellow flag" indicating possibly clinically significant depression (Kroenke et al., 2001; Löwe, Unützer, Callahan, Perkins, & Kroenke, 2004).

### **2.3.7. GAD-7**

Generalized anxiety symptoms will be assessed via the GAD-7 (Spitzer, Kroenke, Williams, & Löwe, 2006) in support of secondary objective 2. Scores range from 0 to 21, with a score of 5 to 9 representing mild anxiety, a score of 10 to 14 representing moderate anxiety, and a score of 15 or greater representing a severe level of anxiety. Scores of 10 or greater are considered a “yellow flag” indicating possibly clinically significant anxiety (<http://www.phqscreeners.com/instructions/instructions.pdf>)

### **2.3.8. SF-12 (Version 2.0)**

The SF-12 is a shortened version of the SF-36, which was designed as a general health utility index. The twelve items provide an estimate for eight domains of functional health and well-being: physical functioning, role-physical, bodily pain, general health, vitality, social functioning, role-emotional, and mental health. Together, the first four domains constitute a Physical Health summary measure, and the second 4 constitute a Mental Health summary measure (Ware, Kosinski, & Keller, 1996). This assessment will be used as a measure of general functioning in support of secondary objective 2.

### **2.3.9. Short pain scale**

Because pain frequently presents with PTSD and may play a confounding role in treatment effectiveness (Asmundson, Coons, Taylor, & Katz, 2002; McGeary, Moore, Vriend, Peterson, & Gatchel, 2011), a 0-10 Likert-type numeric pain scale where 0 represents “No pain,” 5 represents “Moderate pain,” and 10 represents “Worst possible pain” will be administered. The pain scale will be administered in support of secondary objective 2.

Other information that will be collected include:

### **2.3.10. Current Medications**

In order to assess the potential impact of medication use concurrent with study participation, information on prescription psychotropics (including stimulants, anxiolytics, and antidepressants), anticonvulsants, antipsychotics, anticholinergic drugs, opioids, nicotine, sleeping medications, antihypertensives, and sympathomimetics/sympatholytics will be collected.

## **3. STUDY METHOD**

This is a multisite, randomized, blinded, sham-procedure-controlled study to evaluate the effectiveness of unilateral right-sided stellate ganglion block (SGB) on the acute symptomatology of PTSD, evaluated by the CAPS-5 pre-treatment and at 8 weeks. Participants

will be centrally randomized to 2:1 active:sham SGB and will be evaluated at Womack Army Medical Center in North Carolina, Tripler Army Medical Center in Hawaii, and Landstuhl Regional Medical Center in Germany. A total of up to 240 participants will be enrolled at the three sites (up to 80 per site). No single site will enroll more than half the participants and each will have a 2:1 active:sham ratio.

Study intervention will be administered at week 0 and at week 2. Participants will be evaluated for PTSD symptomatology at 0 weeks (pre-treatment) and at 8 weeks using the Clinician-Administered PTSD Scale for DSM-5 (CAPS-5). They will complete the PTSD Checklist for DSM-5 (PCL-5) and the M.I.N.I.-Plus Suicidality Module at 0, 2, 4, 6, and 8 weeks; they also will complete the M.I.N.I.-Plus module at screening. The SF-12, GAD-7, PHQ-9, K6, AUDIT-C/AUDIT, and a short pain scale will be completed at weeks 0, 4, and 8.

#### **4. STUDY POPULATION AND INCLUSION CRITERIA**

Participants will be active duty service members who meet inclusion criteria (as described below):

- Active duty status
- Personal access to Internet
- Anticipated stable assignment to installation for at least 2 months
- Stable dosing for  $\geq 3$  months, if receiving psychotropic medications
- Prior to enrollment, offered PTSD treatment using A-level modality (as defined by MEDCOM policy 14-094; 18 Dec 2014)
- PCL-C score of 32 or greater at screening
- Acceptable clinically indicated preoperative laboratory studies, per standard site-specific protocols

#### **EXCLUSION CRITERIA**

Enrolled subjects must not meet any of the following criteria:

- Prior SGB
- Allergy to amide local anesthetics (e.g., ropivacaine, bupivacaine)
- Pre-existing Horner's syndrome
- Pregnancy

- Current anticoagulant use
- History of a bleeding disorder
- Infection or mass at injection site
- Myocardial infarction within 6 months of procedure
- Phrenic or laryngeal nerve palsy (hoarseness)
- History of glaucoma
- History of schizophrenia, other psychotic disorder, bipolar disorder, or personality disorder (axis 2), as verified by medical record review by an Army Co-Investigator with access to medical records
- Moderate or severe traumatic brain injury as verified by medical record review by an Army Co-Investigator with access to medical records
- Symptoms of moderate to severe substance use disorder in past 30 days
- Suicidal ideation in the past 2 months, documented by the M.I.N.I.-Plus Suicidality Module
- Any ongoing other major life stressor or condition not listed here that the site Investigator believes clearly would place the participant at risk for injury or a poor outcome (including anniversary of the inciting event, pending divorce, undergoing medical board/retirement, undergoing UCMJ or pending legal administrative actions, recent significant illness in participant or family)

## **5. RECRUITMENT**

For recruitment, behavioral health providers (BHP) or family or other physicians within the medical center referral area will identify potential participants and obtain their permission to pass contact information on to the site Research Coordinator (RC). The RC will contact by telephone those who have expressed interest in the study, to explain the study and invite them to participate. The RC will provide a study overview and answer any questions that individuals may have about participation. Once individuals have agreed to take part in the study, they will be asked a few pre-screening questions over the telephone to determine eligibility. Those who pre-screen as eligible will be asked to come to the RC's office to complete the consenting process in person and to complete a computer-based screening, which will assess the study inclusion and exclusion criteria.

## **6. DISCONTINUATION OF INTERVENTION**

Study intervention may be discontinued in the following instances:

- Intercurrent illness that would, in the judgment of the Investigator, affect assessments of clinical status to a significant degree.
- Unacceptable toxicity that compromises the ability to continue study-specific procedures, or is considered to not be in the participant's best interest.
- Participant request to discontinue for any reason.
- Participant non-compliance.
- Pregnancy during the first two weeks of the study, when study-related treatment procedures (either active or sham) are being conducted.
- Discontinuation of the study at the request of the relevant IRB.

## **7. DATA LOCK AND UNMASKING**

Data lock and unmasking will occur after enrollment is completed. The study is designed as intention-to-treat (ITT), and therefore participants will not be excluded after randomization. If a participant discontinues further treatment or participation in the study, for example as a result of an adverse event, every attempt should be made to continue to perform the required study-related follow-up and procedures. If this is not possible or acceptable to the participant or Investigator, the participant may be withdrawn from the study.

## **8. STATISTICAL / ANALYTICAL ISSUES**

### **8.1 Analysis Populations**

This study will have two analysis populations, and intention-to-treat (ITT) population and a per protocol (PP) population.

The primary analysis will be based on the intention-to-treat principle. All participants who were enrolled and randomly allocated to a treatment arm will be included in the analysis in the group to which they were randomized (not to which treatment they actually received). This approach ignores noncompliance, protocol deviations, withdrawal and lost-to-follow-ups. Analysis of the ITT population avoids overoptimistic estimates of the efficacy of an intervention resulting from the removal of non-compliers, accepting that protocol deviations occur in actual clinical practice (Heritier, Gebski, & Keech, 2003).

Analyses will be replicated on the per-protocol population. The per-protocol population will consist of those participants who strictly adhered to the protocol (i.e., will exclude participants that withdrew or were lost-to-follow-up prior to completion of the study, received treatment they were not randomized to, completed visits outside of the prespecified window, participants known to the intervening anesthesiologist, baseline CAPS < 10, screening to baseline interval >32 days, or any other protocol deviation). The per-protocol analysis provides an estimate of the true efficacy of an intervention (i.e., among those who completed the treatment as planned) (Ranganathan, Pramesh, & Aggarwal, 2016).

A sensitivity analysis also will be performed, excluding subjects with final CAPS scores obtained more than 12 weeks post initial intervention and assigning discordant interventions to the one actually delivered.

## **8.2 General Considerations**

Data will be summarized by treatment group. For summaries of study data, categorical measures will be summarized in tables listing the frequency and the percentage of subjects in each treatment; continuous data will be summarized by presenting mean, standard deviation, median and range; and ordinal data will be summarized by only presenting median and range.

Most statistical computations will be performed and data summaries will be created using SAS 9.4. If additional statistical software is required, this will be discussed in the study report. All statistical analyses will be conducted using the intent to treat principle, unless explicitly specified otherwise (e.g., the per-protocol protocol, or for certain secondary and/or post-hoc analyses).

Demographic and all baseline characteristics will be compared between treatment groups. If analyses of these characteristics suggest that substantial differences exist for some of these characteristics between treatments at baseline, their use as covariates will be explored in the model-based secondary analyses.

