## **10. ADVERSE EVENTS**

Reports of adverse events will be collected during the trial, and the Research Monitor is required to review all unanticipated problems involving risk to volunteers or others, Serious Adverse Events (SAE) and all volunteer deaths associated with the protocol and provide an unbiased written report of the event to the USAMRMC Office of Research Protections (ORP) Human Research Protection Office (HRPO).

An adverse event (AE) is any untoward medical occurrence in a clinical investigation participant administered a medicinal product and which does not necessarily have a causal relationship with this treatment. An AE can therefore be any unfavorable and unintended sign, symptom, or disease temporally associated with the use of a medicinal product, whether or not considered related to the medicinal product. AEs may also include pre- or post-treatment complications that occur as a result of protocol-mandated procedures (e.g. invasive procedures such as venipuncture, biopsy, etc.). Pre-existing events, which increase in severity or change in nature during or as a consequence of use of a medicinal product in human clinical trials, will also be considered AEs.

An AE does not include:

- Medical or surgical procedures (e.g. surgery, endoscopy, tooth extraction, transfusion); the condition that leads to the procedure is an adverse event.
- Pre-existing diseases or conditions or laboratory abnormalities present or detected prior to the screening visit, that do not worsen.
- Situations where an untoward medical occurrence has not occurred (e.g. hospitalization for elective surgery, social and/or convenience admissions).
- Overdose of either study drug or concomitant medication without any signs or symptoms unless the participant is hospitalized for observation.

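### The SAP defines no safety population and no adverse event analysis, so under its ITT default adverse events would be counted by assigned arm, not by injection received

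*SAP*

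**What the plan says.** SAP 8.1 names the analysis sets: "This study will have two analysis populations, and intention-to-treat (ITT) population and a per protocol (PP) population". Under ITT, everyone randomised is "included in the analysis in the group to which they were randomized (not to which treatment they actually received". SAP 8.2 then extends this beyond the primary analysis: "All statistical analyses will be conducted using the intent to treat principle, unless explicitly specified otherwise". Its examples of exceptions are the per-protocol analysis and certain secondary or post-hoc analyses; AEs are not among them. The same section says that data are summarised by treatment group, with counts and percentages for categorical measures.

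SAP section 10 opens with "Reports of adverse events will be collected during the trial". It goes on to Research Monitor review, definitions, relatedness and seriousness. It gives no table, rate, denominator, comparison or population, and no departure from 8.2. Protocol section 8 has no AE analysis either, although the synopsis lists adverse events as the criterion for evaluating safety.

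The only as-delivered rule is a sensitivity analysis in SAP 8.1, "excluding subjects with final CAPS scores obtained more than 12 weeks post initial intervention and assigning discordant interventions to the one actually delivered". It is tied to final CAPS scores.

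**The concern.** A safety summary should relate events to what was injected. The SAP's only general rule relates them to what was assigned. The two come apart in two situations.

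- **The wrong injection is given.** A complication of the active block in a sham-assigned participant is then recorded against sham.
- **No injection is given.** The participant stays in the denominator without having been exposed.

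Protocol 7.2 expects the sham injection to carry clearly less risk than the active block and cites a severe complication rate of 0.17% for the latter. With events that rare, one in the wrong column can decide how the severe-event table reads. Clinicians would use that table alongside the efficacy result.

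**Working it through.** **1. Is there a figure to reproduce?** No. The documents state no AE rate, AE denominator or safety sample size.

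**2. Which rule reaches AEs?** Section 10 is silent on analysis, so the general rules of 8.2 apply: summarise by treatment group, using ITT unless an exception is explicit. With ITT as defined in 8.1, this gives events by assigned arm over all randomised participants.

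**3. Can assigned and delivered differ?**

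- *Discordant injections.* SAP 8.1 provides for them twice, in a per-protocol exclusion and in "assigning discordant interventions to the one actually delivered".
- *Randomised but not injected.* Protocol 6.2.1 randomises after the baseline CAPS-5, with week 0 to follow within 4 weeks. At week 0 a positive pregnancy test ends participation (Protocol 6.2.3.1), and a physician may find a participant with a pre-existing Horner's syndrome ineligible (Protocol 6.2.1). SAP section 7 does not exclude participants after randomisation.

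**4. A single event.** Protocol 6.1 plans 160 active and 80 sham. Suppose that one sham-assigned participant receives ropivacaine and has the only complication.

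| Grouping | Active | Sham |
|---|---|---|
| As assigned | 0/160 | 1/80 = 1.25% |
| As delivered | 1/161 = 0.62% | 0/79 |

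**5. Commoner events.** Let pA and pS be the risks after an active and a sham injection. Let k sham-assigned participants receive active and m active-assigned receive sham. Let uA and uS be the numbers never injected, assumed to contribute no events. Then:

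- ITT active = [(160 − m − uA)·pA + m·pS] / 160
- ITT sham = [(80 − k − uS)·pS + k·pA] / 80

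Example with pA = 5%, pS = 1%, k = m = 5 and nobody uninjected: active = (155 × 0.05 + 5 × 0.01)/160 = 4.88%; sham = (75 × 0.01 + 5 × 0.05)/80 = 1.25%; difference 3.6 points against a true 4.0.

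All risks and counts in this table are assumptions. Entries are the ITT risk difference in percentage points.

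| Risks, active v sham | None | 1 swap per arm | 5 swaps per arm | 8 active + 4 sham uninjected |
|---|---|---|---|---|
| 5% v 1% | 4.0 | 3.9 | 3.6 | 3.8 |
| 30% v 10% | 20.0 | 19.6 | 18.1 | 19.0 |

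With swaps alone, the difference is multiplied by 1 − m/160 − k/80. For five per arm this is 1 − 0.031 − 0.063 = 0.906, a loss of about 9%. Leaving 8 and 4 uninjected is 5% of each arm, so both rates and their difference fall by 5% and the risk ratio does not move.

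**6. Severe events.** Read 0.17% as a rate per block (an assumption). Two injections in 160 participants make 320 active blocks. Expected severe complications are 320 × 0.0017 = 0.54, and the chance of at least one is 1 − 0.9983^320 = 42%. The chance that such an event falls in a wrongly injected participant is far smaller. For five sham-assigned participants given active at both visits, it is about 10 × 0.0017 = 1.7%.

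**The case against.** The best reply is that the SAP plans no AE rate, so nothing is misattributed as written, and that the protocol says the trial is not a safety study. Relatedness is judged on actual exposure (Protocol 7.3, SAP 10.1) and the Research Monitor reviews each SAE. The link between a serious event and the injection given therefore does not depend on a by-arm table alone. Much of this stands: the more basic gap is the missing AE analysis, and individual review protects the reading of individual events. It does not supply a rate by injection received, and the only stated default points the other way.

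A reader might go further in three ways that the documents do not support.

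- **That the per-protocol repeat loses AE withdrawals.** SAP 8.1 does say "Analyses will be replicated on the per-protocol population", and that set "will exclude participants that withdrew or were lost-to-follow-up prior to completion of the study, received treatment they were not randomized to". But 8.1 justifies the set as an efficacy estimate, 8.5 and 8.6 apply it to the primary and secondary analyses, and AEs are neither. At most it would add a second table; the ITT table would keep those who withdrew.
- **That every rule favours the active block.** Per-protocol removes cross-overs, and with them this misattribution. Dropping withdrawals has no known direction, and uninjected participants dilute both arms.
- **That a particular share of participants was never injected.** The documents give no figure.

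**Conclusion.** The point holds in a conditional form. The SAP has no safety population and no AE analysis, and its stated default would group AEs by assignment over all randomised participants. Whether that changes any number depends on how many participants receive the other injection or none, which the documents do not report. With none, ITT and as-delivered rates are identical. To say that AE rates *are* misattributed would therefore go too far.

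Under the assumed counts the effect on common events is modest: up to about 9% of the risk difference with five swaps per arm, and 5% with 12 uninjected. For a rare event, one misplaced case can reverse the table, though that is unlikely. The reason to act is that the default is the less suitable rule for the protocol's own safety criterion, and replacing it is easy. It should be changed; it does not threaten the efficacy conclusion.

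**What to change.** - **SAP 8.1:** add a safety population of all participants who received at least one study injection, grouped by the injection actually delivered, with a stated rule for anyone who received both kinds.
- **SAP 10:** state that AEs and SAEs are tabulated in this population by delivered arm, as numbers of participants and of events, and that this is an explicit exception to the ITT default in 8.2.
- **SAP 10:** list separately the AEs that occur before or without any injection. Protocol 7.2 records AEs from after the screening visit, so an injected-only set would otherwise leave these out.

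The delivered injection is already documented (Protocol 5.2 and 9.1.6), so no new data are needed. The cost is a few sentences, one table and one listing. Efficacy analyses are unchanged. If the change is made by addendum after unblinding, it should be marked as such, as the existing addenda are.
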